### 5.3.4 Physical performance-based tests

- The difference between the two treatment groups in the mean ratio between the injured and uninjured side of the timed step test.
- The difference between the two treatment groups in the mean ratio between the injured and uninjured side of the single leg hop tests.

These endpoints will be analysed similarly to the analysis for hamstring muscle strength (see Section 5.3.3).

### 5.3.5 Range of motion

The difference between the two treatment groups in the ratio between the range of motion in knee extension and hip flexion. This endpoint will be analysed similarly to the analysis for hamstring muscle strength (see Section 5.3.3).

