#### 4.2.2.3 Physical performance-based tests of both injured and uninjured leg.

##### Hamstring muscle strength

Maximum isometric force in supine position (see protocol appendices physio protocol and instruction). Study sites equipped with a computer-based isokinetic dynamometer will test maximum isokinetic force during knee flexion and hip extension (see protocol appendices physioprotocol and physioinstruction).

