### 5.3.3 Hamstring muscle strength

The difference between the two treatment groups in the ratio between the injured and uninjured side of the maximum isometric strength in supine position and isokinetic force during knee flexion and hip extension (see protocol appendix physioprotocol and appendix physioinstruction). We will test for differences in the ratio between the groups using a Wilcoxon test, for ease of interpretation. We may also analyse the difference between the groups in a linear regression model, where the dependent variable will be muscle strength in the injured leg, and the independent variable will be muscle strength in the uninjured leg at baseline and the relevant follow-up timepoint, the muscle strength in the injured leg at baseline, site, age, sex, and degree of tendon retraction.

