### 5.3.5 Radiological outcomes

- Difference between groups in the ratio of hamstrings muscle volume and fatty infiltration between the injured and uninjured side measured by MRI at 24 months.
- Ratio of attached tendons at the ischial tuberosity measured by MRI at 24 months.

These endpoints will be analysed similarly to the analysis for hamstring muscle strength (see Section 5.3.3).

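### SAP Section 5.3.5 omits the injured/uninjured comparison, so range of motion reads as a ratio of knee extension to hip flexion

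*SAP*

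**What the plan says.** Section 5.3.5 (Range of motion; the number is used again for the radiological outcomes) defines the endpoint in one sentence: "The difference between the two treatment groups in the ratio between the range of motion in knee extension and hip flexion". The only two quantities named are two movements. Neither leg is mentioned. The section then refers to Section 5.3.3 for the analysis.

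The related parts of the SAP read differently:

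- Section 4.2.2.3 has the heading "Physical performance-based tests of both injured and uninjured leg". Range of motion is listed beneath it, as hip flexion and knee extension, with no ratio between them.
- Section 5.3.3 compares arms on "the ratio between the injured and uninjured side of the maximum isometric strength in supine position", and likewise for isokinetic force. On the test it says: "We will test for differences in the ratio between the groups using a Wilcoxon test, for ease of interpretation". A regression with the injured leg as outcome and the uninjured leg as a covariate is optional.
- Section 5.3.4 uses "the mean ratio between the injured and uninjured side of the timed step test" and the same form for the hop tests.
- Section 5.3.5 (Radiological outcomes) takes muscle volume and fatty infiltration as a ratio "between the injured and uninjured side measured by MRI at 24 months".

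**The concern.** A programmer who follows the sentence would divide knee extension by hip flexion and would have to choose the leg. That number is not a measure of recovery. It compares two movements that the injury may affect together, and it drops the internal control, the uninjured leg, on which the neighbouring endpoints rely.

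At stake is whether the range-of-motion comparison can be interpreted. An arm that had lost the same share of both movements would look unaffected. An arm that had lost mainly hip flexion would show a higher ratio, the same direction as a gain in knee extension. A programmer who instead guesses the intended meaning must still decide whether there is one endpoint or two, and which leg goes in the numerator.

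**Working it through.** The SAP gives no figure for this endpoint, so there is nothing to reproduce. The check has three parts.

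**1. Algebra.** Let KE and HF be knee extension and hip flexion in the injured leg, with proportional losses a and b. Then

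(KE(1-a)) / (HF(1-b)) = (KE/HF) × (1-a)/(1-b).

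If the two legs were equal before injury, the injured/uninjured ratios are simply 1-a and 1-b.

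| Loss KE / HF | Factor on KE/HF | Injured/uninjured KE | Injured/uninjured HF |
|---|---|---|---|
| 10% / 10% | 1.00 | 0.90 | 0.90 |
| 20% / 20% | 1.00 | 0.80 | 0.80 |
| 20% / 10% | 0.889 | 0.80 | 0.90 |
| 10% / 20% | 1.125 | 0.90 | 0.80 |
| 20% / 0% | 0.80 | 0.80 | 1.00 |
| 0% / 20% | 1.25 | 1.00 | 0.80 |

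With assumed angles of 80 and 110 degrees, 80/110 = 0.727. A 20% loss in both gives 64/88 = 0.727. A 20% loss in hip flexion alone gives 80/88 = 0.909.

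**2. How far the cancellation reaches.** It is exact only when a = b. Equal losses in degrees generally do not cancel. Taking 15 degrees off both movements, the factor on KE/HF under assumed starting values is:

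- 80/120: (65/105)/(80/120) = 0.929
- 70/110: (55/95)/(70/110) = 0.910
- 160/110: (145/95)/(160/110) = 1.049
- 120/120: 1.00

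**3. Simulated rejection rates** of a two-sided 5% Wilcoxon test, 50 patients per arm (the number required before drop-out in Section 6.2), 2,000 runs, with the loss in the injured leg of one arm. Assumed, not from the SAP: log-normal values, coefficient of variation 10%, correlation 0.8 between legs and 0.3 between movements.

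| Loss KE / HF | KE/HF, injured leg | Injured/uninjured KE | Injured/uninjured HF |
|---|---|---|---|
| none | 6.60% | 5.40% | 4.55% |
| 5% / 5% | 4.35% | 97.95% | 97.65% |
| 10% / 10% | 5.10% | 100% | 100% |
| 10% / 5% | 59.75% | 100% | 97.65% |
| 10% / 0% | 99.00% | 100% | 5.05% |

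The top three rows are all null cases for KE/HF. Their mean is (6.60 + 4.35 + 5.10)/3 = 5.35%, which is chance level. In the last two rows KE/HF does respond, but as part 1 shows, the sign of the response depends on which movement lost more.

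**The case against.** The strongest reply is that this is a slip of the pen and that the intent can be recovered. Section 5.3.3 has the same sentence shape: a ratio between sides, followed by two movements joined by 'and' as a list. Removing the side phrase leaves the form found in Section 5.3.5. The reference to Section 5.3.3 leads to an injured/uninjured ratio and to a regression that makes sense only with both legs. Most of this stands, and dropped words are the likely explanation. It does not remove the defect. Section 5.3.4 carries the same reference and still states the sides, as does the radiological section for muscle volume and fatty infiltration, so the SAP does not normally leave the variable to be inferred from it. The regression is optional.

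Three stronger readings are tempting, and the document supports none of them:

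- A reader might infer that any loss in both joints goes undetected. That is true only for equal proportional losses.
- A reader might infer that the sponsor chose a knee-to-hip ratio as the endpoint. The two-leg heading, the separate listing of the movements and the neighbouring definitions all point the other way.
- A reader might infer that a ratio is unusable because normal knee extension could be recorded near 0 degrees, so that a difference in degrees is required. The recording convention is in protocol appendices that are not at hand, so this cannot be settled here.

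**Conclusion.** The sentence in Section 5.3.5 is wrong as written and should be corrected. It states a rule which, if followed, gives a variable that conflicts with Section 4.2.2.3 and with the parallel endpoints, that ignores equal proportional losses, and whose direction cannot be read as benefit or harm when losses differ.

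The algebra needs no assumption beyond the literal reading. The example angles and the simulation rest on assumed values and only illustrate the point. The reach is limited to one secondary endpoint; the primary PHAT analysis is untouched. Whether any reported result is affected depends on which variable was computed, and the SAP does not say.

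**What to change.** Reword Section 5.3.5 (Range of motion) to define two endpoints, hip flexion and knee extension. Each is the ratio of the injured to the uninjured side, compared between arms with the Wilcoxon test of Section 5.3.3. State for each which direction is worse. Use the side-to-side difference in degrees only if the recorded values can be at or near zero, which the physiotherapy appendices should show.

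Section 7 already describes completed analyses in the past tense, and the SAP is at version 1.6. The change should therefore be entered in the revision history as a clarification, with a statement of which range-of-motion variable was actually analysed. If that was knee extension over hip flexion, the per-movement comparison should be run and reported as a correction.

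The cost is a few lines of text and no new data, since both legs are already tested. The downside is that one secondary comparison becomes two.

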### 5.3.5 Radiological outcomes

- Difference between groups in the ratio of hamstrings muscle volume and fatty infiltration between the injured and uninjured side measured by MRI at 24 months.
- Ratio of attached tendons at the ischial tuberosity measured by MRI at 24 months.

These endpoints will be analysed similarly to the analysis for hamstring muscle strength (see Section 5.3.3).

## 5.5 Descriptive analyses

### 5.5.1 Trial flowchart

The flow of participants through the trial will be summarized using a CONSORT diagram. The flow diagrams will describe the numbers of participants randomly allocated, who received allocation, withdrew consent, and included in the ITT, PP, and AS analysis populations. Also the observational cohort may be depicted in the flowchart.

### 5.5.2 Baseline characteristics

Baseline characteristics will be described descriptively and will include:

- Age
- Sex

- Injured leg
- BMI
- Occupational level
- Activity at injury
- PHAT
- LEFS
- IPAQ-SF
- Degree of tendon retraction
- Number of tendons detached (conjoint, semimembranosus or both)
- Time to treatment, (days)

Summary statistics will be used for each variable: median and interquartile ranges for continuous variables, and number and percentages for categorical variables.

### 5.5.3 Trajectories – display of results over time

We may produce graphs to show the trajectory of individual patients and the randomized arms (as well as the observational cohort) with respect to the follow-up of endpoints (primary as well as secondary) over time.

## 5.6 Subgroups

Results may be stratified by the following subgroups:

- Site
- Age
- Sex
- Degree of tendon retraction
- Number of tendons detached (conjoint, semimembranosus or both)

## 5.7 Missing data

All reasonable efforts will be taken to ensure that the level of missing data and loss to follow-up will be minimal.

Missing data can occur in different ways in the study: (1) individual questions in the instruments (e.g. the PHAT questionnaire) can be left unanswered; (2) data on specific endpoints may be entirely missing at different follow-up timepoints (due to a e.g. a functional test not being performed or data on a specific instrument not collected); and (3) patients can miss specific follow-up visits or drop out of the study altogether (resulting in no information on endpoint data for the corresponding follow-up timepoint or missing data on all subsequent follow-up timepoints).

Missing data on individual instrument (e.g. PHAT) questions will be imputed using predictive mean matching (PMM), with donor pool (k)=5.

Missed follow-up visit at specific follow-up timepoints will be handled using a multiple imputation by chained equations (MICE). The multiple imputation protocol will be based on models for predicting outcomes at specific follow-up timepoints based on outcomes data recorded at other time points together with treatment group, patient age, sex and degree of tendon retraction. For example, a missing PHAT score at 24 months will be imputed based on a regression model fit to

data from timepoints 3, 6, and 12 together with treatment group, patient age, sex and degree of tendon retraction.

We will generate 1,000 datasets with imputed outcome data, which will be analyzed separately. We will then use Rubin's rules to pool the estimated absolute differences in PHAT score and standard errors.

The global COVID pandemic has occurred during the conduct of this trial. COVID and restrictions have had a major impact on the healthcare situation and has resulted in rescheduled and cancelled follow-up visits in PHACT. Therefore, visits will be analyzed as follows:

- Visits occurring 2.5 to 4.5 months after randomization (or baseline for the observational cohort) will be considered as the 3 month visit.
- Visits occurring 4.5 to 9 months after randomization (or baseline for the observational cohort) will be considered as the 6 month visit.
- Visits occurring 9 to 18 months after randomization (or baseline for the observational cohort) will be considered as the 12 month visit.
- Visits occurring >18 months after randomization (or baseline for the observational cohort) will be considered as the 24 month visit. If there are several such visit, the one closest to the 24 month mark will be used.

Since the date for PROM reporting, MRI, and physiotherapy visits may differ, we will use the data if the primary endpoint (PHAT) reporting for the grouping.

## 5.8 Additional analyses

### 5.8.1 Heterogeneous treatment effects

We will test for heterogeneity of treatment effects by testing for significant interactions (following the best practices described in Wang et al. *N Engl J Med* 2007; 357:2189-2194) in the following subgroups: tendon retraction  $>2$  versus  $\leq 2$  cm and age  $>50$  versus  $\leq 50$  years and IPAQ score above or below the median IPAQ at baseline (median computed across the two randomized arms).

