## 6.2 Updated sample size calculations (181204)

The study progress and accrual are continuously monitored. Specifically, we have pre-specified an evaluation of the study after 60 included participants with a possible increase in the size of the study as a result of the evaluation if it is motivated by a greater dropout than expected or new vital information obtained from discussions with patients and clinical staff. The study has in December 2018 been ongoing for 14 months and about 50 patients have been included in the study. It is clear that our original estimate of the incidence of the injury was too low. We also conclude that the logistics and operational aspects of the study are well-functioning. Thus, we have the possibility to consider an increase in the size of the study. The study has a unique opportunity to answer not only the primary question but also to analyze the effect of age and the severity of the injury on the effect of the two treatments.

To do this, we have discussed the ethical aspects of such a change:

Pros:

- A larger number of patients in the study increases the power of the study; i.e. reduces the risk of type 2 errors.
- A larger number of patients provides a better basis for subgroup analyzes. This is something that in conversations with patients has emerged as a crucial aspect, as a specific patient is interested in the probable outcome for him or her (i.e. patients who have the same characteristics) rather than the overall result at the population level.

Cons:

If the study in its current form can deliver a clear result that affects the treatment of future patients, the dissemination of result will be delayed by the study becoming larger and a number of patients will be treated without the new knowledge being reported. We believe that this risk is limited and justified. Based on clinical experience and existing scientific literature, there are no indications that the treatment result differs clearly between the groups and a larger study size provides a greater opportunity for results that are conclusive and lead to a change in clinical practice.

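### If the heterogeneity tests in SAP 5.8.1 use the PHAT values imputed under 5.7, the treatment-by-subgroup interactions are pulled towards zero, because the imputation model specifies none of them

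*SAP*

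**What the plan says.** Section 5.8.1 commits to the interaction tests: "We will test for heterogeneity of treatment effects by testing for significant interactions". The subgroups are retraction above 2 cm, age above 50 years, and "IPAQ score above or below the median IPAQ at baseline (median computed across the two randomized arms"). The section names neither the endpoint nor the data set.

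Section 5.7 gives the rule for missed visits: "Missed follow-up visit at specific follow-up timepoints will be handled using a multiple imputation by chained equations (MICE"). It is not limited to the primary analysis. The imputation models are "based on outcomes data recorded at other time points together with treatment group, patient age, sex and degree of tendon retraction". The worked example, a missing 24-month PHAT, repeats the list: "data from timepoints 3, 6, and 12 together with treatment group, patient age, sex and degree of tendon retraction". Treatment group is a predictor, so imputation is not done separately by arm. No product terms are listed, and neither is IPAQ. Then: "We will generate 1,000 datasets with imputed outcome data, which will be analyzed separately". What is pooled is also stated: "We will then use Rubin's rules to pool the estimated absolute differences in PHAT score and standard errors".

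Section 6.2 gives, as one reason for enlarging the trial, the chance to "analyze the effect of age and the severity of the injury on the effect of the two treatments".

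**The concern.** An imputation model should contain the structure that the analysis will test. If it has treatment and age but not their product, each missing score is drawn as if the treatment effect were the same at all ages, except for what the patient's own earlier scores carry. Adding those draws to the observed data dilutes any true interaction. Generating 1,000 data sets does not help, because the fault lies in the model and not in the number of draws. For IPAQ, both the variable and its product with treatment are absent.

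At stake is how a non-significant test is read. It could be taken to show that one treatment suits all ages and injury severities, when part of the result comes from the imputation. Two of the three tests, on age and retraction, address the question that 6.2 uses to justify the larger trial.

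**Working it through.** **Inputs from the SAP.** 60 patients per arm, SD 20, and dropout of 0, 10 or 20% (6.2, Table 1).

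**Assumed, because the SAP does not give them.** Equal correlation of 0.6 between visits, a true 24-month interaction of 20 points, a 50/50 subgroup split, and data missing completely at random. The interaction at months 3, 6 and 12 is taken as full throughout, growing (25, 50, 75, then 100%), or absent before month 24.

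**Table 1 first.** Power = Φ(10 / (SD·√(2/n)) − z), with SD 20 and one-sided alpha 0.05:
- n = 60: 10/3.651 − 1.645 = 1.094, giving 86.3% (SAP 85)
- n = 54: 10/3.849 − 1.645 = 0.953, giving 83.0% (SAP 82)
- n = 48: 10/4.082 − 1.645 = 0.805, giving 78.9% (SAP 79)

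All 12 rows agree within 2 points, so the inputs are read correctly.

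**Size of the pull, by formula.** Let d be the share with 24-month PHAT missing and c the share of the interaction that the patient's observed earlier scores carry into the imputed value. The recovered share is about 1 − d(1 − c). With k earlier visits observed, each has regression weight ρ/(1 + (k−1)ρ). For k = 3 this is 0.6/2.2 = 0.273.
- Only month 24 missing, interaction full throughout: c = 3 × 0.273 = 0.818. Recovered 1 − 0.1 × 0.182 = 0.982 at 10% and 1 − 0.2 × 0.182 = 0.964 at 20%.
- Only month 24 missing, interaction growing: c = 0.273 × (0.25 + 0.50 + 0.75) = 0.409. Recovered 0.941 and 0.882.
- No follow-up at all, or interaction only at month 24: c = 0. Recovered 0.90 and 0.80.

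The formula is approximate, since the weights shift slightly when the product is left out.

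**Large-sample simulation (n = 400,000).** The recovered share with treatment and subgroup as main effects was:

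| Missing pattern | Interaction | 10% missing | 20% missing |
|---|---|---|---|
| Month 24 only | full | 0.979 | 0.969 |
| Month 24 only | growing | 0.944 | 0.886 |
| Month 24 only | late | 0.906 | 0.799 |
| Staggered dropout | full | 0.955 | 0.919 |
| Staggered dropout | growing | 0.927 | 0.845 |
| Staggered dropout | late | 0.899 | 0.802 |
| No follow-up | all three | 0.895-0.906 | 0.795-0.807 |

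Leaving the subgroup variable out altogether (the IPAQ case) gives nearly the same figures. So what matters is the missing product with treatment; an IPAQ main effect alone would not repair it. With the product included, recovery is 99-101% throughout.

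**Power at n = 120.** Interaction of 20 points growing over visits, two-sided 5%, 20 imputations, 600 trials, Monte Carlo error about 2 points:

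| Setting | Complete data | Complete cases | Imputed, no product | Imputed, with product |
|---|---|---|---|---|
| 10%, staggered | 73.3 | 69.7 | 64.2-64.5 | 70.7 |
| 10%, no follow-up | 75.8 | 70.3 | 60.5-61.5 | 69.8 |
| 20%, staggered | 73.5 | 65.3 | 52.8-53.3 | 67.5 |
| 20%, no follow-up | 75.5 | 67.2 | 46.8-47.7 | 65.8 |

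The two figures in the fourth column are with and without the subgroup main effect. The loss due to the imputation model is the last column minus the fourth: about 6, 8-9, 14-15 and 18-19 points. A second simulation under the same assumptions gave 4-9 points at 10% and 7-17 at 20%. In these settings imputation without the product did worse than complete cases.

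**With no true interaction** (20% staggered), the test rejected in 1.8-2.0% of trials, against 4.3% with complete data and 2.8% with the product included. With 600 trials the gap to 2.8% is not firm.

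**The case against.** **The link to imputed data is inferred.** Section 5.8.1 does not say that it uses the imputed data sets, and the pooled quantity named in 5.7 is the PHAT difference, which is the main contrast. A reader might conclude that the SAP states these tests run on imputed values. It does not. The link stands only as the natural reading of a general rule, with no other missing-data rule covering 5.8.1.

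**The list does not fix a functional form.** A reader might say that 5.7 prescribes main effects only. It lists variables and does not exclude products. What can be said is that no interaction is specified and that IPAQ is not on the list.

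**Not all lost power is due to the imputation.** At 20% dropout with no follow-up, power falls from 75.5% with complete data to about 47%. It is tempting to charge all 28 points to the imputation. About 10 of them (75.5 − 65.8) are lost even with the correct model, because data are missing. The fair comparator is imputation with the product.

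**The inputs favour a visible effect.** Twenty points is one assumed SD and twice the non-inferiority margin. For 10 points, the standard error of 20 × √(4/30) = 7.30 gives only about 28% power with complete data. A simulation with 10-20% missing gave 17-25% without the product and 23-28% with it. At that size a non-significant test mainly reflects sample size. The largest bias also needs dropouts with no follow-up PHAT, or an interaction that appears only at month 24, and the SAP does not say that either is expected.

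**The error is conservative.** It creates no false subgroup claims, and the tests are additional analyses. Both points are correct and limit the weight of the matter.

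**Conclusion.** The point holds conditionally. If 5.8.1 uses the 5.7 data sets with the listed predictors and nothing more, its interaction estimates are biased towards zero. That direction follows from the specification. The size does not: the ranges of 2-10% at 10% missing and 3-20% at 20% missing, and the power loss of a few points up to about 17-19, rest on the assumed correlation, interaction size and time course, and missingness completely at random. If few 24-month values are missing, the effect is negligible.

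A reader might go further and infer that the primary result is biased, or that any null subgroup finding is an artefact. Neither is supported. The main treatment contrast is untouched by this point, and small interactions would usually be missed at this sample size with complete data too. It is still worth correcting, because 6.2 uses the age and severity question to justify the larger trial and the correction is cheap.

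**What to change.** State in 5.7 or 5.8.1 which data set the heterogeneity tests use. If it is imputed data, then for those tests add baseline IPAQ and the products of treatment with age, retraction and IPAQ to the imputation model, coded at the cut-points that are tested. Use the same imputed sets for all three tests. Imputing within each randomised arm, with baseline IPAQ and the cut-point indicators as predictors, is the alternative.

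The cost is a sentence or two and a re-run, with no new data. The drawbacks are a little more imputation noise and a second set of imputed PHAT values beside those used for the primary contrast. Imputation by arm fits each model on at most about 60 patients. In a separate simulation with 15-20% missing, it recovered 94-100% of the complete-data interaction with IPAQ added, so the product terms are the lighter choice. If the tests have already been run, the re-run belongs in section 7 as a labelled post-hoc analysis.
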